TC4

true

2018-09-29T14:39:55-05:00

Ticagrelor compared to clopidogrel in acute coronary syndromes - the TC4 comparative effectiveness study

TC4 Research Protocol

Submitted to McGill University REB Dec 11 2018 (updated)

Amendment Oct 29 2019

Funded by Canadian Health Research

Hypothesis to be tested

We are proposing a novel randomized clinical trial (RCT) to investigate which dual antiplatelet therapy (DAPT) strategy is superior following an acute coronary syndrome (ACS). The trial acronym, a necessity for all good trials (!), is TC4 (Ticagrelor compared to clopidogrel in ACS).

Our null hypothesis is that there will be no clinical differences in CV outcomes between patients randomized to ticagrelor or clopidogrel.

Specific goals to be investigated are as follows;

1. The primary objective will compare the composite outcome of total mortality, myocardial infarction (MI), or stroke at 12 months in the two treatment arms (primary hypothesis).
2. A secondary objective will compare the individual outcomes of total mortality, acute MI stroke, major bleeding requiring hospitalization, recurrent coronary revascularizations, patient drug compliance and drug side effects at 12 months in the two treatment arms (secondary hypothesis).
3. A secondary objective will compare the primary outcome according to gender at 12 months in the two treatment arms (secondary hypothesis).
4. A tertiary objective will compare the composite outcome of total mortality and rehospitalization for acute MI at 36 months in the two treatment arms (tertiary hypothesis not to be funded with this grant proposal).
5. Another tertiary objective will be to perform a quality of life and cost-effectiveness of the competing interventions (tertiary hypothesis not to be funded with this grant proposal).

Knowledge to date

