A major driver of standard RCT costs is the expense of securing long term follow-up. To overcome this barrier and the vexing potential bias of lost to follow-up, we will use the novel “randomized registry” design. An early example of this design involved a non-industry sponsored, multicenter, prospective, randomized, controlled, open-label clinical trial of manual thrombus aspiration in 7244 Swedish STEMI patients undergoing PCI[23]. In this remarkable trial, over 80% of all eligible patients were recruited and the trial took only 1 year to complete. The data were monitored and adjudicated as part of a regular registry validation. A NEJM editorial[24] called this the next disruptive technology in clinical research by allowing high quality trials to be successfully and rapidly completed at a small fraction of the usual cost.

Our study will employ baseline CRXO randomization (to avoid indication bias) with follow-up using the administrative database environment of the hospital electronic medical records and the universal Quebec healthcare system, which provides validated long-term follow-up of meaningful health outcomes of all patients[25-27] at minimal costs and with which the PI has a vast experience[28-31]. Moreover, these

databases will permit the acquisition of long term outcomes (beyond 12 months) which have been previously lacking in virtually all ACS trials. More specific details on patient side effects will be obtained via the hospital's electronic medical record and data warehouse which has been built using a CFI grant.

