All patients hospitalized for an ACS, with or without ST-segment elevation, will be eligible to participate. For STEMI and NSTEMI positive biomarkers and appropriate ECG changes will be required. NSTEMI patients with negative biomarkers are generally considered as unstable angina and will also be eligible for study inclusion if their treating physician has determined that DAPT is appropriate. It is important to note that the entrance criteria of this study are well aligned with those of PLATO allowing synthesis of the totality of the evidence (see analysis section below).

The intervention

Patients will be randomly assigned to receive standard doses of ticagrelor or clopidogrel. Ticagrelor will be given according to PLATO dose[9] of a 180 mg loading dose followed by 90 mg BID. Clopidogrel patients will receive a 300-mg loading dose followed by 75 mg daily. All patients will receive aspirin loading dose of 325 mg followed by 81 mg daily. Patients will be encouraged to take their DAPT medication for 12 months. Patient compliance will be monitored electronically via the provincial drug formulary. This will allow for the assessment for any specific DAPT interactions, particularly with anticoagulants. This is of clinical importance since bleeding is the main adverse outcome associated with DAPT.

[figure not shown]
Study outcomes

The main outcome will be a composite of total mortality, myocardial infarction (MI), or stroke at 12 months (PLATO primary outcome). Secondary outcomes will be cardiovascular mortality, stroke, major bleeding requiring hospitalization, recurrent coronary revascularizations, patient compliance and drug side effects. Clinical events will be independently assessed from hospital and provincial electronic health records which have been previously validated for these outcomes[25-27]. Data extraction will be by blinded observers so the initial unblinding of treatment assignment should not result in bias. At the time of consent, patients

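### Read literally, the only named bleeding outcome leaves out major bleeds during the index hospital stay

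*Protocol*

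**What the plan says.** The restriction appears twice. The secondary objective under Hypothesis to be tested lists "major bleeding requiring hospitalization, recurrent coronary revascularizations, patient drug compliance and drug side effects at 12 months in the two treatment arms". The Study outcomes section repeats it: "Secondary outcomes will be cardiovascular mortality, stroke, major bleeding requiring hospitalization". No other bleeding outcome is named.

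On when exposure starts, the Study population section says: "All patients hospitalized for an ACS, with or without ST-segment elevation, will be eligible to participate". The intervention section says: "Patients will be randomly assigned to receive standard doses of ticagrelor or clopidogrel", and goes on to give a loading dose for each study drug and for aspirin. The same section gives the reason for watching bleeding: "bleeding is the main adverse outcome associated with DAPT".

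On data sources, Study outcomes says: "Clinical events will be independently assessed from hospital and provincial electronic health records". The Methods section adds: "More specific details on patient side effects will be obtained via the hospital's electronic medical record and data warehouse". The October 2019 amendment says that follow-up comes from provincial records and that there are no research visits.

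**The concern.** A bleed in a patient who is already an inpatient complicates an admission but does not cause one. If the outcome counts only bleeds that lead to hospitalization, it can in effect be met only after discharge, although assignment and exposure start before it. The uncounted window covers the loading phase and, at a centre described as a high-volume PCI hub, the procedural phase.

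Two things are at stake. Absolute major-bleeding rates over 12 months would be too low in both arms. A difference between the drugs in early major bleeding would not show in the comparison meant to detect it. The definition also fits poorly with the section on possible problems, which relies on the databases to pick up every adverse event of clinical importance.

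**Working it through.** **Reading the text.** The protocol states no bleeding rate, effect size or power, so there is no figure to reproduce. The check is whether any part of the protocol brings index-stay bleeds back into the outcome.

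1. Both definitions carry the same restriction to bleeds needing hospitalization.
2. Eligible patients are those already hospitalized, and treatment opens with loading doses.
3. No section adds in-hospital bleeds, bleeds that prolong the stay, or fatal in-hospital bleeds to this outcome.
4. The hospital record is named as a source for clinical events and for side effects. The omission therefore comes from the definition, not from a general lack of data.

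**Effect on the absolute rate.** Let f be the share of 12-month major bleeds that occur in the index stay. The counted rate is (1 − f) × the true rate. The documents do not give f or the true rate. Take 4,000 patients (Sample size calculations) and assume a true rate of 3%, which is 120 events:

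| Assumed f | Events counted | Reported rate |
|---|---|---|
| 0 | 120 | 3.0% |
| 20% | 96 | 2.4% |
| 30% | 84 | 2.1% |
| 50% | 60 | 1.5% |

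**Effect on the comparison.** Keep the 120 assumed events, with f = 50%. Let a and b be the events in the two equal arms, ignore clustering, and use z = ln(b/a) / √(1/a + 1/b). Three assumed patterns:

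| Pattern | Index stay | After discharge | Post-discharge only | Combined |
|---|---|---|---|---|
| Same ratio throughout | 22.5 v 37.5 | 22.5 v 37.5 | ratio 1.67, z = 0.511/0.267 = 1.92 | 45 v 75: ratio 1.67, z = 0.511/0.189 = 2.71 |
| Difference only after discharge | 30 v 30 | 22.5 v 37.5 | ratio 1.67, z = 1.92 | 52.5 v 67.5: ratio 1.29, z = 0.251/0.184 = 1.37 |
| Difference only in index stay | 22.5 v 37.5 | 30 v 30 | ratio 1.00, z = 0 | 52.5 v 67.5: ratio 1.29, z = 1.37 |

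Under the first pattern, leaving out index-stay bleeds widens the log-scale interval by 1/√(1 − f) − 1. That is 12%, 20% and 41% for f = 20%, 30% and 50%. Under the second, leaving them out gives the clearer signal. Under the third, the early difference disappears. The direction of the effect on power therefore depends on a pattern that the documents do not describe.

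**The case against.** The other side has several fair points.

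- **The exclusion is inferred.** No sentence expressly excludes index-stay bleeds. The phrase could be a severity threshold, meaning a bleed bad enough to need hospital care, and no start date after discharge is set. This stands as a limit on certainty. But the restriction is written into the protocol twice, so it is more than a detail left to the analysis plan, and on its plain wording two extractors could code the same bleed differently.
- **The outcome's rank.** A reader might take this to be the trial's main safety outcome. The protocol does not say so. It is one of several secondary outcomes, and the remark about bleeding describes the drugs without ranking the endpoints.
- **Other routes of capture.** A reader might infer that the whole safety comparison ignores the loading and procedural phase. That goes too far: drug side effects is a separate secondary outcome drawing on the hospital record, and a fatal bleed counts in total mortality. What remains is that these bleeds do not enter the major-bleeding comparison.
- **The record may be incomplete.** The recruiting hospital section says that 7-8 community hospitals refer their ACS patients. If a stay begins elsewhere, this hospital's record may not hold the early bleeds. This stands, and the fix must allow for it.
- **The restriction may be deliberate.** Admission for bleeding is an objective event that a database can find, which suits an open-label trial without visits. This is plausible, but the protocol does not give it as a reason.
- **Dilution.** Procedural bleeds unrelated to drug choice can weaken the combined ratio, as the second pattern shows. This stands, and is why the parts should be reported separately.

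**Conclusion.** The point holds as a defect in the definition of one secondary outcome. Read literally, the only named bleeding outcome leaves out major bleeds during the index stay, and nothing else in the protocol restores them to that comparison. Major-bleeding rates from treatment start would be understated by the index-stay share: by 20% to 50% in relative terms if that share is 20% to 50%, which is an assumption. An early drug difference in major bleeding could be missed.

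It would be tempting to add that the trial loses a known amount of power for bleeding. The documents do not support that: they give no bleeding rate, no share of bleeds in the index stay and no early or late effect, and the calculation can go either way. The primary outcome is not affected. The definition should be settled before outcome extraction, because the amendment's reliance on provincial follow-up records could otherwise make later admissions the default.

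**What to change.** Define the outcome as major bleeding from the first study dose that either occurs during the index stay or leads to a later hospitalization. Take index-stay events from the hospital record, adding provincial records for any part of the stay spent at a referring hospital. Take later events from provincial admissions. Report the index-stay, post-discharge and combined results by arm. Use the same wording in the objectives and in Study outcomes.

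The cost is one definition and one more item in an extraction that is already planned. There is a small downside: two data sources then feed one outcome, and procedural bleeds unrelated to drug choice may pull the combined ratio towards 1. Reporting the parts separately makes both visible and keeps the post-discharge result available as now defined. No treatment or clinical rule changes.

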will also be consented to consult their electronic health records at 1 and 3 years post randomization. The ability to measure long term outcomes at 3 years, via electronic databases, is another distinctive aspect of the study and will offer a unique opportunity to assess the long term consequences of different DAPT strategies following an ACS. While the main objective of this project is the evaluation of clinical effectiveness and safety outcomes, the expertise of the team will permit future ancillary investigations into quality of life and economic sub-studies. The project will also provide unique training and research opportunities for graduate students.

Sample size calculations

As there is some similarity between individuals within the same cluster, both within the same time period and across different time periods, CR trials require an increased sample size compared to a standard individual parallel group RCT. This loss of efficiency is more than offset by a more comprehensive patient recruitment. In addition to effect size and variation, CRXO sample size calculation depends upon the number of clusters, the size of the clusters, the number of time periods, and the similarity between individuals (both within and between clusters) as measured by the ICC. Assuming the event rates recorded in PLATO (12% vs. 10%), type 1 and type 2 errors of 5% and 20% respectively, power calculations for a standard individual randomized trial approach would suggest the need for 1,500 patients in each arm. For a CR trial, calculations using R (library(CRTsize) suggests that we need 6 clusters of 400 patients for each arm (total 4800, larger sample size due to ICC). However CRXO design has been shown to increase the statistical efficiency over the standard CR design[22]. The Figure below shows that 5 clusters for each arm (total sample size 4000) will provide greater than 80% power[21], suggesting that our 18-month recruitment period will be sufficient. Given our current annual angiogram / PCI volume and with the expected additional 10% of potential recruited ACS patients coming from the hospital CCU without an angiogram, we should have the capacity to meet our power calculations within an 18 month recruitment period based on the excellent (>90%) recruitment rates observed in other pragmatic comparative effectiveness trials[36].

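### For 12% vs 10% the plan's 1,500 per arm should be about 3,841 two-sided (3,026 one-sided), so 4,000 patients give at most about 52% power (65% one-sided), not over 80%

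*Protocol*

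**What the plan says.** The Sample size calculations section of the protocol sets its inputs as follows: "Assuming the event rates recorded in PLATO (12% vs. 10%), type 1 and type 2 errors of 5% and 20% respectively". It builds three figures on them.

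- Individually randomised trial: "power calculations for a standard individual randomized trial approach would suggest the need for 1,500 patients in each arm".
- Parallel cluster trial: "we need 6 clusters of 400 patients for each arm (total 4800, larger sample size due to ICC").
- Cluster crossover, the chosen design: "5 clusters for each arm (total sample size 4000) will provide greater than 80% power".

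The same section says that cluster trials need more patients than individually randomised ones. It concludes that 18 months of recruitment will be enough. It closes by saying that using the 1,800 PLATO North American patients as the prior adds a margin of over 50% to the calculation. Neither the sidedness of the test nor a value for the intraclass correlation (ICC) appears in the text.

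**The concern.** A two-point difference around an 11% event rate is small, and 1,500 per arm is far too few to detect it with 80% power. The two later figures fail the same test: both the 4,800 and the 4,000 lie below what an unclustered trial would need. The section thus contradicts its own premise that clustering raises the sample size.

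The power claim is what supports the recruitment target and the statement that the trial can detect the PLATO effect. If true power is nearer one half, an inconclusive stand-alone result is quite likely even if that effect is real. Anyone relying on the stated power could give such a result too much weight.

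**Working it through.** **Inputs.** All from Sample size calculations: p1 = 0.12, p2 = 0.10, type 1 error 5%, power 80%, equal arms. Sidedness is not stated. The hypothesis section ("Our null hypothesis is that there will be no clinical differences in CV outcomes between patients randomized to ticagrelor or clopidogrel") and the open question of which regimen is superior point to two-sided, so that is taken as the main case, with one-sided alongside.

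**Trying to reproduce 1,500 per arm.** Pooled two-proportion formula:

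n per arm = [z_a × √(2 × 0.11 × 0.89) + 0.842 × √(0.12 × 0.88 + 0.10 × 0.90)]² / 0.02²

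- Two-sided (z_a = 1.960): (0.8673 + 0.3722)² / 0.0004 = 3,841 per arm, 7,682 in total.
- One-sided (z_a = 1.645): (0.7278 + 0.3722)² / 0.0004 = 3,026 per arm, 6,052 in total.

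Other two-sided versions give 3,838 (unpooled), 3,835 (arcsine) and 3,941 (continuity correction). Event-based formulas at the 11% mean event rate, for hazard ratios from 0.824 to 0.84, give about 3,820 to 4,720 per arm two-sided and 3,010 to 3,720 one-sided. Swapping the two error rates gives 4,190 two-sided and 3,025 one-sided. None gives 1,500 per arm.

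**Power at the stated sizes.** Power = Φ[(0.02 − z_a × SE0) / SE1], with SE0 = √(2 × 0.11 × 0.89 / n) and SE1 = √((0.1056 + 0.0900) / n). For n = 2,000 per arm, SE0 = 0.009894 and SE1 = 0.009889. Two-sided: Φ(0.061) = 52%. One-sided: Φ(0.377) = 65%.

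| Per arm | Total | Two-sided | One-sided |
|---|---|---|---|
| 1,500 | 3,000 | 42% | 54% |
| 2,000 | 4,000 | 52% | 65% |
| 2,400 | 4,800 | 60% | 72% |

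**The cluster total.** With a parallel-cluster design effect of 1 + (m − 1) × ICC, any ICC of zero or more gives a total of at least 7,682 two-sided (6,052 one-sided). The stated 4,800 is below both.

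**The crossover.** Its design effect is about 1 + (m − 1) × ICC_within − m × ICC_between. Taking the between-period correlation to be no larger than the within-period one, the smallest value is 1 − ICC, in effect 1. For 2,000 per arm to reach 80% power, the design effect would have to be 2,000 / 3,841 = 0.52 two-sided, or 2,000 / 3,026 = 0.66 one-sided. A crossover cannot supply that, so 52% (65%) is in effect a ceiling.

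**Detectable difference at 2,000 per arm, two-sided.** For 12% vs 9.27%, SE0 = 0.00975 and SE1 = 0.00974, so (0.0273 − 1.960 × 0.00975) / 0.00974 = 0.84, which is 80% power. The trial is therefore sized for about 12% vs 9.3%, before clustering.

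**Clustering loss, illustration only.** With assumed ICCs, m = 400 and no recovery from the crossover, two-sided power at 2,000 per arm falls to 45% at ICC 0.0005 (design effect 1.20) and 40% at ICC 0.001 (design effect 1.40).

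**The PLATO margin.** Counting all 1,800 North American patients as fully concordant data gives 5,800 in total, or 2,900 per arm. Two-sided: Φ(0.474) = 68%. One-sided: Φ(0.790) = 79%.

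**The case against.** **Sidedness.** The protocol never says that the test is two-sided, so a flat ceiling of 52% is more than it fixes. This stands: 52% is conditional on two-sided testing and 65% is the one-sided counterpart. Neither comes near the stated power.

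**Rounding.** The PLATO rates may have been rounded. At the extreme, 12.5% vs 9.5%, two-sided testing still needs 1,707 per arm. Only one-sided testing (1,345) would then fit within 1,500. Those rates imply a ratio of 9.5 / 12.5 = 0.76, against the hazard ratio of 0.84 that the protocol reports for PLATO, so rounding is not a credible rescue.

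**The missing figure and ICC.** The power curve behind the crossover claim is not shown and no ICC is given in the text. Neither matters for the ceiling, which holds for any non-negative ICC.

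**The Bayesian primary analysis.** The Statistical analysis section makes a synthesis with PLATO data primary, and the section on possible problems says the evidence will be read together with what already exists. This weakens the idea that a null result will be taken as proof of no difference. It does not repair the power figure, which is claimed for the trial's own 4,000 patients, and a stand-alone analysis is also promised. Nor are the North American patients concordant with the assumed effect: the protocol reports a hazard ratio of 1.25 for them.

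**Stronger readings.** A reader might divide 2,400 by 1,500, obtain a design effect of 1.6, infer an ICC of 0.0015, and quote a power of 29% from a t-test on ten period summaries with 8 degrees of freedom. The protocol does not support this. The ratio is of two figures that are themselves wrong, the planned models are generalized estimating equations and hierarchical models, and the design allows 6 to 10 periods. A reader might also note that half of the one-sided per-arm number is about 1,513 and conclude that a per-arm number was read as a total. That is possible, but the document does not show it and the point does not need it.

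**Conclusion.** The point holds. The 1,500 per arm is too small by a factor of about 2.6 two-sided (3,841 / 1,500) or 2.0 one-sided (3,026 / 1,500). The 4,800 contradicts the section's own premise about clustering, and the over-80% power for 4,000 patients cannot be reached at 12% vs 10%.

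The supportable statement is a power of at most about 52% two-sided, or 65% one-sided, before any clustering loss. It rests on the protocol's event rates and error rates, equal arms, a binary outcome at 12 months, and a between-period correlation no larger than the within-period one. The actual loss from clustering cannot be fixed from the document, because it depends on ICCs that are not given.

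**What to change.** In Sample size calculations:

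- State the sidedness; two-sided is the natural reading of the hypothesis section.
- Replace 1,500 per arm by 3,841 (or 3,026 if one-sided testing is declared).
- Remove the 4,800 figure and the over-80% power statement.
- Give the power of 4,000 patients as at most about 52% two-sided, with a detectable difference of about 12% vs 9.3%, both before clustering.
- Show any clustering loss only as a sensitivity range over ICCs declared as assumptions, under the planned analysis models.
- Correct the closing safety-margin sentence: even as fully concordant data, the 1,800 PLATO patients bring the total to 5,800 and power to about 68% two-sided (79% one-sided).
- Add that an inconclusive stand-alone result is not evidence of equivalence.

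This is a rewording of one section. It needs no extra enrolment and no change to the design or to the Bayesian analysis. The cost is a less favourable stated power.

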However, a large multicenter RCT (PLATO)[9] showed a statistically significant decrease in composite CV outcomes with the newer ticagrelor compared to clopidogrel. This has prompted both European[6] and Canadian[8] guideline writers to endorse ticagrelor / aspirin as the DAPT of choice. However residual uncertainties regarding the choice of DAPT are highlighted by the PLATO subgroup analysis[9] that showed an increased risk with ticagrelor in North America (NA) patients. This led to delayed FDA approval, dissenting FDA reviews[10] and an unwillingness of US guidelines [7] to recommend the ticagrelor DAPT regime over others.

[figure not shown]
2) The specific need for another DAPT RCT Do we really need a replication study after an 18,000 patient RCT showed a statistically significant decrease in composite CV outcomes? Unfortunately, as I have demonstrated in two peer review publications, the answer is an unequivocal yes[11, 12]. While the integrity of the PLATO data has been questioned by some [13-15], the main area of uncertainty, at least from a NA perspective, hinges on the small number of NA patients randomized in this trial and their increased risk with ticagrelor (n=1814, HR 1.25; 95% CI 0.93 - 1.67). The risk in NA patients was statistically significantly different from the benefit seen in the other subgroups (p=0.04) and the crux of the debate is then whether to believe the subgroup analysis or the combined study results (n=18624, HR, 0.84; 95% CI 0.77 to 0.92). The complete study provides maximal information but perhaps at a cost of being less representative of what to expect in NA practice. Conventional statistical paradigms would say that given the pre-specified nature of the geographic subgroup analysis and given the statistically significant interaction observed, one should concentrate on the subgroup results and not the combined results.

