In addition to a standalone analysis, our main Bayesian analysis will incorporate the 1800 PLATO NA patients as our prior distribution, essentially providing a > 50% safety margin for our sample size calculations (see next section).

Statistical analysis

[figure not shown]
The trial data will be analyzed following the intention to treat principal. Clustered data require appropriate advanced statistical techniques that accounts for the likeness of cluster members, otherwise analysis can lead to overly precise estimates and potentially incorrect inferences about the effectiveness of the intervention.

Appropriate analysis will involve generalized estimating equations and hierarchical models. Bayesian analyses will be performed using JAGS [37] version 3.4.0 and R [38]. All Markov Chain Monte Carlo simulations will be run on two chains with 10 000 iterations discarding the first 1000. Convergence will be monitored using CODA [39] and checked by observing the traces of posterior samples, and by inspecting the Gelman-Rubin R statistic [40] and the Raftery-Louis diagnostics.[41]

Our primary analysis will involve a Bayesian approach that synthesizes all the pertinent evidence concerning these DAPT regimes by incorporating our prior information (PLATO data) with the likelihood of the current data. The advantages of this approach include a mathematically rigorous and exact combination of the totality of the data allowing direct probability statements about the relative strengths of the two regimes (statements that are desired by clinicians and decision-makers but which are technically impossible with the usual frequentist (p value) approach). The strength of this approach is displayed graphically and is described more fully in the next section. We will also perform a “standalone” Bayesian analysis by using a non-informative prior so that results driven uniquely by the data from this proposal may be appreciated.

Anticipated results and conclusions

Concretely the question remains which PLATO data shall we use for the prior data, the whole dataset or that limited to the NA subgroup. Our Bayesian approach will examine the robustness of the data by considering both! First, consider in the Figure (top) what might be called the “enthusiastic” prior which uses all the data and shows the overall benefit with ticagrelor.

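### The PLATO North American prior is called a sample-size safety margin, but it opposes the planned effect and lowers the chance of showing it

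*Protocol*

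**What the plan says.** The Sample size calculations section starts from "Assuming the event rates recorded in PLATO (12% vs. 10%), type 1 and type 2 errors of 5% and 20% respectively", and states that "5 clusters for each arm (total sample size 4000) will provide greater than 80% power". Its closing paragraph mentions a standalone analysis and then adds that "our main Bayesian analysis will incorporate the 1800 PLATO NA patients as our prior distribution, essentially providing a > 50% safety margin".

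The subgroup behind that prior is described under The specific need for another DAPT RCT, where its result is given as "increased risk with ticagrelor (n=1814, HR 1.25; 95% CI 0.93 - 1.67". The whole-trial PLATO result in the same place is "n=18624, HR, 0.84; 95% CI 0.77 to 0.92".

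Statistical analysis makes the PLATO-informed Bayesian analysis primary and adds a standalone one with a non-informative prior. Anticipated results and conclusions then asks again which PLATO data should form the prior and answers that both will be used: the whole dataset (labelled enthusiastic) and the North American subgroup (labelled skeptical). It illustrates each prior only with 1,500 new patients whose results agree with it. From those two cases it infers that any other pairing of prior and new data should also be conclusive.

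**The concern.** Prior patients act like extra sample size only if their result points the same way as the effect to be shown. The planning rates assume that ticagrelor lowers risk; the North American subgroup suggests that it raises risk. Adding the second to a trial sized for the first pulls the posterior away from the planned effect, so what is described as a reserve is a cost.

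At stake is what the reader believes about the primary analysis. Anyone relying on the sample size section would think the design has power to spare and could tolerate under-recruitment. If the North American prior carries the conclusion, the planned effect would seldom be confirmed, and a finding for clopidogrel would come more easily even if the drugs were equal.

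**Working it through.** **Inputs**
- Planning rates 12% and 10% (Sample size calculations). Ticagrelor is taken as the 10% arm because PLATO's overall HR is 0.84. HR = ln(0.90)/ln(0.88) = 0.824, log HR -0.193; risk ratio 0.10/0.12 = 0.833, log -0.182.
- Planned size 4,000, so 2,000 per arm: about 240 and 200 events.
- North American prior: HR 1.25 (0.93 to 1.67).
- Assumed, because the protocol states neither: a conclusion is drawn when the posterior probability of superiority exceeds 97.5% (95% as a check), and there is no clustering penalty, which favours the protocol.

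**The plan's own figures first.** The protocol says that "power calculations for a standard individual randomized trial approach would suggest the need for 1,500 patients in each arm". For two proportions, two-sided 5%, 80% power:

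n = [1.96·√(2·0.11·0.89) + 0.842·√(0.12·0.88 + 0.10·0.90)]² / 0.02² = 3,841 per arm (one-sided: 3,026).

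The stated 1,500 is not reproduced. Power at 2,000 per arm is 52% two-sided (65% one-sided), not above 80%. That is a separate issue; it matters here only because it sets the flat-prior baseline.

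**Prior and likelihood on the log HR scale**
- Prior mean ln 1.25 = 0.223; SD = (ln 1.67 - ln 0.93)/3.92 = 0.149; precision 44.8, worth about 4/0.149² ≈ 179 events.
- Trial SE = √(1/240 + 1/200) = 0.0957; precision 109.1.
- Posterior SD = 1/√(44.8 + 109.1) = 0.0806; posterior mean = (44.8·0.223 + 109.1·x)/153.9, where x is the observed log HR.

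**Observed result needed at 97.5%**
- Ticagrelor superior: x < (-1.96·0.0806·153.9 - 10.0)/109.1 = -0.315, HR below 0.73. Flat prior: x < -1.96·0.0957 = -0.188, HR below 0.83.
- Clopidogrel superior: x > (24.3 - 10.0)/109.1 = 0.131, HR above 1.14. Flat prior: x > 0.188, HR above 1.21.

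**Chance of each conclusion**

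| Truth | Conclusion | Flat, 97.5% | NA prior, 97.5% | Flat, 95% | NA prior, 95% |
|---|---|---|---|---|---|
| 12% vs 10%, as HR 0.824 | ticagrelor superior | 52% | 10% | 65% | 19% |
| 12% vs 10%, as ratio 0.833 | ticagrelor superior | 48% | 8% | 60% | 16% |
| HR 1.0 | clopidogrel superior | 2.5% | 8.5% | 5% | 16% |
| HR 1.25 | clopidogrel superior | 64% | 83% | 75% | 91% |

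Example: Φ[(-0.315 + 0.193)/0.0957] = Φ(-1.27) = 10%.

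**In patients.** For an 80% chance of showing the planned effect on the HR scale, the flat prior needs about 3,850 per arm and the North American prior about 5,970. The ratio is 5,970/3,850 = 1.55, so the prior adds about 55% to the required size.

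**Clustering.** With an assumed design effect of 1.5, the flat and North American figures at HR 0.824 and 97.5% become 38% and 2%; with 2.0, 30% and under 1%.

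**The omitted pairing.** Take the North American prior and suppose all 4,000 patients reproduce PLATO's overall HR of 0.84 (x = -0.174). Posterior mean = (10.0 - 19.0)/153.9 = -0.0586: HR 0.94 (0.81 to 1.10), with P(HR<1) = Φ(0.0586/0.0806) = 77%. That is not conclusive.

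**The case against.** **The prior is not firmly fixed.** This stands. The sample size section attaches the word main to the North American prior, but the later text promises both PLATO priors, and a non-informative analysis is planned too. A reader might infer that the trial's primary analysis has only about a 10% chance of showing its planned effect. The documents do not support that as a flat statement: the figure belongs to one announced analysis. At the planned effect and 97.5%, whole PLATO at full weight (0.84, 0.77 to 0.92) makes success near certain. The protocol's hierarchical estimate (0.86, 0.49 to 1.60) gives about 55%, hardly different from flat. The safety-margin sentence, however, is tied explicitly to the North American patients.

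**The threshold is assumed.** This also stands, and the 2.5% and 8.5% figures apply a frequentist calibration that the protocol does not set for its Bayesian analysis. At 95% the levels change but the direction and the rough size of the loss do not.

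**The prior can help.** It does if ticagrelor is truly harmful, a possibility the protocol takes seriously. The gain is conditional on direction, and it is not the direction the trial was sized for.

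**A skeptical prior is legitimate.** Agreed. The protocol argues for it from a pre-specified subgroup with a significant interaction. A reader might infer that it must be replaced by a shrunken estimate. That is a modelling choice, and the protocol gives no shrunken North American figure. But a skeptical prior costs power for the planned effect and cannot also be counted as reserve.

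**The percentage itself.** It is tempting to call the 50% an arithmetic slip, since 1,800/4,000 = 45% and only 1,800/3,000 = 60% exceeds it. The sentence points forward to a section whose illustrations use 1,500 of 4,000 patients, so the figure may not be a patient ratio at all. Nothing here rests on it.

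**Conclusion.** The point holds in this form: for the effect the trial is sized on, the North American prior is not a safety margin. It lowers the chance of concluding for ticagrelor to roughly a fifth of the flat-prior value at a 97.5% threshold, and to between a quarter and a third at 95%. It also makes a clopidogrel conclusion more than three times as likely when the drugs are equal, and it helps only under ticagrelor harm. The assurance about all remaining pairings of prior and data is wrong as well, as the 77% example shows.

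The figures rest on a normal approximation, the prior at full weight, an assumed decision threshold and no loss from clustering; any such loss makes the result worse. The documents do not show that the North American prior alone will decide the trial or that using it is improper. They do leave unsettled which prior decides, and the conclusion can turn on that choice.

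**What to change.** - Delete the safety-margin claim from Sample size calculations, and the claim in Anticipated results and conclusions that every other pairing of prior and data should be conclusive. Count no PLATO patients towards power.
- State which announced prior (North American, whole PLATO or non-informative) carries the primary conclusion. If it is whole PLATO, say whether at full weight or in its between-region form.
- For every announced prior, report the probability of concluding for ticagrelor, for clopidogrel and for neither at HR 0.82, 1.0 and 1.25, with the posterior threshold and the clustering assumption stated.
- A shrunken North American prior may be added as a sensitivity analysis; it is not required.

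The cost is a short calculation and a less favourable stated margin. No patients or new data are needed. Naming the primary prior is a decision about the analysis rather than wording, so it should be recorded before the follow-up outcomes are merged with the baseline data.
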